**A Randomized Trial to Improve Quality of Life in
People with Cirrhosis – the Mi-Kristal RCT**

IRB Approval Date: December 1, 2021

NCT05061992

**A Randomized Trial to Improve Quality of Life in People with Cirrhosis –
the Mi-Kristal RCT**

Principal Investigator (PI):

[name]

Division of Gastroenterology and Hepatology
Department of Internal Medicine
University of Michigan, Ann Arbor, MI

Correspondence:

[name]

[name]

[name]

P: [contact]

F: [contact]

e: [contact]

Key words: Cirrhosis, Hepatic Encephalopathy, Liver Disease

Disclosures: No conflicts of interest to disclose

SUMMARY

Study Name	A Randomized Trial to Improve Quality of Life in People with Cirrhosis – the Mi-Kristal RCT
Subject Population	At least 50 patients with cirrhosis and portal hypertension, with no previous lactulose use, and moderate to high self-reported daily activity impairment.
Objective	To determine if lactulose therapy improves health-related quality of life (HRQOL), cognitive function, sleep quality and activity level impairment and reduces number of falls.
Design	Randomized two-arm study of lactulose
Arms	Treatment: Crystalized Lactulose (Kristalose) Control: No intervention
Procedures	
- Screen cirrhosis patients and determine if they meet inclusion and exclusion criteria.- Determine regular daily activity level impairment using WPAI; consent and randomize patients.- Collect demographic information and conduct baseline assessments: questionnaires assessing HRQOL, cognitive function, sleep quality, health history and current alcohol use.- Randomized subjects receive 28 days of crystallized lactulose therapy (20g twice daily (b.i.d.)) or no therapy.- Automated SMS or email follow-up at 3, 6, 9, 14, 15, 21 and 28 days with patients in treatment group: assess bowel movements; may be done via email or phone if required.- 28-day follow-up evaluation consists of questionnaires assessing HRQOL, cognitive function, sleep quality, falls and activity level impairment.
Site	Michigan Medicine, Ann Arbor, MI

Table of Contents

SIGNIFICANCE	5
1. STUDY OBJECTIVES	5
1.1 Specific Aims	5
1.1.1 Primary Aims	5
1.1.2 Secondary Aims	5
1.2 End Points	6
2. STUDY DESIGN	6
3. SELECTION AND ENROLLMENT OF SUBJECTS	7
3.1 Inclusion Criteria	7
3.2 Exclusion Criteria.....	7
3.3 Study Enrollment Procedures	8

3.3.1 Identification & Recruitment.....	8
3.3.2 Monitoring of Recruitment Targets	8

HE is caused by brain exposure to ammonia, a waste product of bacterial metabolism in the gut. Normally the liver converts ammonia to urea. Unfortunately, owing to technical challenges in its measurement and confounding factors in the pathogenesis of HE, the level of ammonia in the blood is a poor biomarker for the risk or presence of HE. Leveraging the concept that HE presents as a spectrum with early, subclinical stages presenting with poor quality of life (QOL), we have used the presence of poor QOL to predict the development of HE.(15) We have found that answers to a one-question 0-10 scale rating the impact of cirrhosis on one's daily activity efficiently distinguishes patients with low 1-year risk of HE from those with high risk.(15) In clinical practice many clinicians detect disturbances in QOL or functioning that could be associated with HE and empirically start HE-directed therapy. In this trial we will extend our prior research by enrolling patients at high risk of overt HE and formally test the benefits of QOL-triggered HE therapy.

1. STUDY OBJECTIVES

The primary objective is to determine whether lactulose therapy in a study population of cirrhosis patients with portal hypertension improves their health-related quality of life (HRQOL). We will be using crystalized lactulose (Kristalose, Cumberland Pharmaceuticals). We have 6 specific aims, which are detailed below

1.1 SPECIFIC AIMS

1.1.1 Primary Aim

Aim 1: To determine whether lactulose therapy improves self-reported HRQOL as assessed using the Short Form-8 Health Survey (SF-8).

1a. Comparison of SF-8 scores from baseline to 28 days, between the intervention and control arm.

1.1.2 Secondary Aim

Secondary aim of this trial include:

Aim 2: To determine whether lactulose therapy improves cognitive function as assessed using the Animal Naming Test (ANT).

2a. Comparison of ANT scores from baseline to 28 days, between the intervention and control arm.

1.1.3 Exploratory Aims

Aim 3: To determine whether lactulose therapy improves overall sleep quality as assessed using the Pittsburgh Sleep Quality Index (PSQI).

3a. Comparison of PSQI overall sleep quality ratings from baseline to 28 days, between the intervention and control arm.

Aim 4: To determine whether lactulose therapy improves regular daily activity impairment as assessed using the Work Productivity and Activity Impairment Questionnaire (WPAI).

4a. Comparison of self-reported regular daily activity impairment scores as part of WPAI from baseline to 28 days, between the intervention and control arm.

1.1.3 Exploratory Adverse Event Aims

Aim 5: To determine if lactulose therapy increases the incidence of >5 self-reported bowel movements per day.

5a. Comparison of self-reported episodes of >5 daily bowel movements from baseline to 28 days between the intervention and control arm.

Aim 6: To determine if lactulose therapy reduces the number of self-reported falls.

6a. Comparison of self-reported number of falls from baseline to 28 days between the treatment and control arm.

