1.2 END POINTS

All patients will be followed until death, liver transplantation or final study visit at 28 days post – enrollment.

Primary Endpoint

1. Comparison of SF-8 at 28 days post-baseline, between the two groups.

Secondary Endpoints

1. Comparison of ANT, overall sleep quality, regular daily activity impairment, falls, and average number of daily bowel movements at 28 days, compared between the two groups.

[figure not shown]

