4.3.2 Adherence Assessment

During the 28-day intervention phase, all subjects will be contacted on Study Days 3, 6, 9, 14, 15, 21 and 28 via automated REDCap email or SMS text messages via Twilio service. Study Day 28 will only be collected via REDCap email or phone. These points of contact are to collect data about stool frequency and consistency among all subjects and therefore lactulose adherence in the treatment group. If the subject opts out of Twilio service, the subject can also receive these questions via REDCap automated email or a study coordinator will collect this data from the subject directly via phone or email. On Study Days 3, 6, 9, 14, 21 and 28 subjects will be asked the following questions:

1. "How many bowel movements did you have yesterday? Please respond with a whole number." *If 0-4 bowel movements are reported the subject will exit the survey. If >4, the subject will receive the following instructions:*

Since you had > 4 bowel movements yesterday, please reduce to **one** 20g dose of kristalose (1 packet) packet per day. Please call the study line at [contact] if you continue to have more than 4 bowel movements daily or with any questions or concerns.

On Study Day 15 subjects will be asked:

2. "Please reference the Bristol Stool Chart we provided to you to answer this question. How would you describe your stool looks today? Please respond with the applicable number, between 1-7. *All subjects exit survey after response.*

1. Separate hard lumps
2. Sausage-shaped but lumpy
3. Like a sausage but with cracks on its surface
4. Like a sausage or snake, smooth and soft
5. Soft blobs with clear cut edges
6. Fluffy pieces with ragged edges, a mushy stool
7. Watery, no solid pieces, entirely liquid

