6.2 QUANTITATIVE ANALYSIS

We will compare differences in all outcomes, each continuous variable, using MANOVA. Multiple linear regression will be used to adjust for baseline covariates.

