17.1 If yes, number of falls: _____

18. What is the current (past 2 weeks) average number of bowel movements you have per day?

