18.1 If yes, number of falls: _____

4. What is the current average number of bowel movements you have per day? _____

5. During the past seven days, how much did your CIRRHOSIS affect your ability to do your regular daily activities, other than work at a job?

By regular activities we mean the usual activities you do, such as work around the house, shopping, childcare, exercising, studying, etc. Think about times you were limited in the amount or kind of activities you could do and times you accomplished less than you would like. If CIRRHOSIS affected your daily activities only a little, choose a low number. Choose a high number if CIRRHOSIS affected your activities a great deal.

CIRRHOSIS had no effect on my work

CIRRHOSIS completely prevented me from working

0 1 2 3 4 5 6 7 8 9 10

CIRCLE A NUMBER

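### Aim 5 asks how often bowel movements exceed 5 per day, but the listed endpoint is a Day 28 average, and the sections disagree on whether controls give daily counts

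*Combined protocol and SAP*

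**What the plan says.** Section 1.1.3 (Exploratory Adverse Event Aims) states Aim 5 as "To determine if lactulose therapy increases the incidence of >5 self-reported bowel movements per day". Aim 5a makes it operational as "Comparison of self-reported episodes of >5 daily bowel movements from baseline to 28 days", between the two arms.

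Section 1.2 has no episode endpoint. Its secondary list gives "average number of daily bowel movements at 28 days, compared between the two groups". Bowel movements are thus exploratory in one section and secondary in the other.

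Bowel data are collected in three places:
- **Baseline, Appendix B item 18:** "What is the current (past 2 weeks) average number of bowel movements you have per day".
- **Day 28, Appendix G item 4:** "What is the current average number of bowel movements you have per day", with no recall period.
- **On study, section 4.3.2, Days 3, 6, 9, 14, 21 and 28:** "How many bowel movements did you have yesterday? Please respond with a whole number". Replies above 4 trigger an instruction about study drug.

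Section 4.3.2 sends these surveys to all subjects. The Summary describes them for the treatment group, and section 7.4 for the intervention groups. Section 6.2 describes all outcomes as "each continuous variable, using MANOVA", with linear regression for covariate adjustment.

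**The concern.** The aim is about how often a threshold is crossed, and the endpoint is about average frequency. No section links the two, names the surveys as the source for Aim 5, or says how an unanswered survey counts. The analysis section offers no method for a count or a proportion.

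Two things are at stake. If the plan is followed as listed, the trial reports a difference in averages and leaves open whether lactulose makes days above 5 more common. If the analyst notices the gap later, the episode variable would be chosen after the data are in. In addition, if controls are not surveyed there is nothing to compare the treated arm's episodes with.

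**Working it through.** The plan gives no rate, effect or precision for Aim 5, so there is no figure to reproduce. The sample size in section 6.1 concerns quality of life. The check is whether each item collected can supply the quantity in Aim 5a.

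**1. Does the average determine the episode rate?** No. Two patterns with the same mean show this without any distributional assumption:
- 3 per day on every day: mean 3, share of days above 5 = 0%.
- 7 on one day in five, 2 on the others: mean = 0.2 × 7 + 0.8 × 2 = 1.4 + 1.6 = 3, share of days above 5 = 20%.

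**2. Is there a baseline episode count?** No. Item 18 of Appendix B is an average over two weeks, and by step 1 it cannot be turned into episodes. A change from baseline in episodes is therefore unavailable. The Day 28 item drops the two-week recall, so even the averages are not asked in the same way at the two visits.

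**3. Is there an on-study episode count?** Yes, on a sample of days. The whole number reported on each of six survey days can be classed as above 5 or not. That samples 6/28 = 21% of days and gives 0 to 6 episodes per subject.

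**4. In which arms?** The sections conflict:

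| Place | Who receives the surveys |
|---|---|
| Section 4.3.2 | All subjects |
| Summary | Treatment group |
| Section 7.4 | Intervention groups |
| Section 2 | Controls described only as completing baseline and Day 28 assessments |
| Table 1 | Message row not split by arm |

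Section 7.4 also lists Day 9 twice and omits Day 6, so the set of days needs reconciling too.

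**5. How much do six looks show?** This is an illustration only. The documents give no daily mean, so assume independent Poisson counts with mean m:

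p = P(X > 5) = 1 − Σ(k = 0 to 5) e^(−m) m^k / k!, and P(at least one such day in six) = 1 − (1 − p)^6.

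| Assumed m | p per day | At least one in 6 looks | At least one in 28 days |
|---|---|---|---|
| 2 | 1.7% | 9.5% | 37% |
| 3 | 8.4% | 41% | 91% |
| 4 | 21.5% | 77% | nearly 100% |

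For m = 3: e^(−3) × 18.4 = 0.916, so p = 0.084 and 1 − 0.916^6 = 0.41. The spread across m shows how strongly the result depends on the assumption. Differences between subjects, and dose reduction after a high count, would change these figures.

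**The case against.** The best reply is that Aim 5a can be carried out. Read in full, it is a comparison between randomized arms, and the phrase about baseline to 28 days can mean the observation window. An incidence compared between randomized arms needs no baseline count, and section 4.3.2 supplies whole-number daily counts. This stands. A reader might infer that the comparison cannot be computed at all; the documents do not support that. Only the change-from-baseline reading fails. The window reading is not settled either. Aims 2a to 4a use the same phrase for measures taken at both visits, and the falls in Aim 6a do have a baseline count (Appendix B item 17.1).

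A reader might also treat the survey's branch at more than 4 as a competing outcome definition. It is not: it triggers an instruction after the number is given, and any cut can be applied to the recorded number.

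One could also cut the reported average at 5, which is possible at both visits. That counts subjects with a high average, not episodes, and the plan does not propose it.

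Finally, episodes and averages can both be reported, and sampling six days does not by itself bias the share of days above 5 if both arms follow the same schedule. Both points are fair, but the plan lists only the average and leaves the arms surveyed unclear.

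**Conclusion.** The listed endpoint and analysis do not answer Aim 5. That conclusion rests on the wording of sections 1.1.3, 1.2 and 6.2 and on the arithmetic in step 1, not on any assumed distribution. A between-arm comparison of on-study episodes is feasible from data that section 4.3.2 already plans, provided controls are surveyed. If the Summary and section 7.4 describe what is done, there are no control-arm daily counts and the comparison fails.

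The impact is low. The aim is labelled exploratory, nothing in the documents makes it the trial's main tolerability question, and the SF-8 comparison is untouched. The percentages for six looks (about 10%, 41% and 77% for assumed means of 2, 3 and 4 per day) are illustrative and predict nothing about this trial.

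**What to change.** - **Outcome (sections 1.1.3 and 1.2):** define Aim 5 as the proportion of answered survey days (3, 6, 9, 14, 21, 28) with more than 5 bowel movements. Reword Aim 5a so that it cannot be read as a change from baseline. Give the outcome one label, exploratory or secondary, in both sections.
- **Analysis (section 6.2):** compare arms with a binomial model clustered by subject, or compare subject-level proportions. Exclude unanswered days from the denominator and report the number of answered days by arm.
- **Arms and days:** reconcile the Summary and section 7.4 with section 4.3.2 so that both arms are surveyed on the same days. The instruction that follows a reply above 4 refers to study drug, so its text needs reconciling with the control arm.
- **Average:** keep the Day 28 average as a separate outcome, and add the two-week recall to Appendix G item 4 to match baseline.

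The cost is protocol wording, one questionnaire phrase and one simple analysis, plus messaging to controls if it was not already intended. Six sampled days per subject give limited precision, and the fix does not change that.

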1.2 END POINTS

All patients will be followed until death, liver transplantation or final study visit at 28 days post – enrollment.

Primary Endpoint

1. Comparison of SF-8 at 28 days post-baseline, between the two groups.

Secondary Endpoints

1. Comparison of ANT, overall sleep quality, regular daily activity impairment, falls, and average number of daily bowel movements at 28 days, compared between the two groups.

[figure not shown]

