6. STATISTICAL CONSIDERATIONS

6.1 SAMPLE SIZE AND ACCRUAL

While no studies of lactulose enrolling patients exclusively with deficits in quality of life, one high quality study of lactulose therapy have been performed for patients with cognitive dysfunction defined by psychometric testing. Lactulose was associated with a 6.81 95%CI (5.2-8.4) point or 65% relative improvement in health-related quality of life using the Sickness Impact Profile compared to control. Given this magnitude of effect, very few patients need to be enrolled. However, if we hypothesize an attenuated effect (30% improvement), seeking to enroll with a 1:1 randomization, assuming an alpha of 0.05, we will have 90% power to detect a difference among 42 subjects. We will therefore proceed with a study of 50 patients to allow for additional adjustment of baseline covariates and drop-outs.

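### The primary SF-8 outcome can be read as a change or as a Day-28 value, and Section 6.2 does not settle which; naming baseline SF-8 as a covariate would remove the ambiguity and gain power

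*Combined protocol and SAP*

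**What the plan says.** The primary outcome is worded in two places.

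- Section 1.1.1, Aim 1a: "Comparison of SF-8 scores from baseline to 28 days, between the intervention and control arm".
- Section 1.2, primary endpoint: "Comparison of SF-8 at 28 days post-baseline, between the two groups".

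The secondary aim follows the first pattern, "Comparison of ANT scores from baseline to 28 days, between the intervention and control arm", while Section 1.2 lists ANT among outcomes compared at 28 days. Sleep quality (Aim 3a) and WPAI activity impairment (Aim 4a) are split in the same way.

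Section 6.2 is two sentences long. One compares differences in all outcomes by MANOVA. The other adds multiple linear regression to adjust for baseline covariates, none of which is named. Section 6.1 justifies going from 42 to 50 patients partly by that adjustment.

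Table 1 shows SF-8 and ANT at entry and at Day 28. The WPAI score is taken at screening (Appendix F) and in the follow-up questionnaire.

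**The concern.** A change score and a Day-28 score are different variables. Their unadjusted treatment estimates differ by the between-arm difference in baseline means, which in a trial of this size is not negligible. If both wordings stand, either can be reported as the primary endpoint once the data are known, and the stated 5% error rate then no longer describes the procedure.

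There is also a loss of precision. A final value ignores baseline. A raw change subtracts all of it, which over-corrects whenever the correlation between the two measurements is below 1. Regression on baseline estimates the right amount to subtract.

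**Working it through.** **Inputs from the documents.** About 25 completers per arm (Section 2); 1:1 allocation, alpha 0.05, 90% power and 42 subjects (Section 6.1). Sidedness is not stated; two-sided is assumed.

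**Inputs that are assumptions.** The documents give no SF-8 SD, no effect in SF-8 units and no correlation between baseline and Day 28. The effect is therefore written as d, the true difference divided by the SD of one SF-8 measurement, and varied from 0 to 1.0. The correlation ρ is set to 0.3, 0.5 and 0.7.

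**1. The plan's own figure.** Section 6.1 states: "assuming an alpha of 0.05, we will have 90% power to detect a difference among 42 subjects". This cannot be reproduced forwards, because the planned 30% improvement is scaled from a result on the Sickness Impact Profile and no SD is given. Solved backwards with 21 per arm:

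d = (1.960 + 1.282) × √(2/21) = 3.242 × 0.309 = 1.00

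The t-based value is 1.03; a one-sided test would give 0.90. So the sample size implies an effect of roughly 1 SD.

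**2. Chance baseline imbalance.** The between-arm difference in baseline means has SD √(2/25) = 0.28, in units of one SF-8 SD. It exceeds 0.3 SD in either direction in about 29% of trials.

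**3. How the estimates relate.** With equal SDs at both times, and relative to the standard error of the final-value comparison:

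- change: √(2(1−ρ)) = 1.18, 1.00, 0.77 for ρ = 0.3, 0.5, 0.7;
- Day-28 value adjusted for baseline: √(1−ρ²) = 0.95, 0.87, 0.71.

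The final-value and change estimates correlate at √((1−ρ)/2) = 0.59, 0.50, 0.39, so they can easily fall on opposite sides of p = 0.05.

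**4. Simulation.** Bivariate normal scores, 25 per arm, 200,000 trials per setting (simulation error about 0.1 percentage point), each analysed by a t test on Day-28 values, a t test on change, and regression of the Day-28 value on arm and baseline. Entries are percentages for ρ = 0.3 / 0.5 / 0.7.

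| True effect (SD) | Readings disagree on p<0.05 | Significant: final value | Significant: change | Significant: adjusted for baseline |
|---|---|---|---|---|
| 0 | 8 / 8 / 9 | 5 | 5 | 5 |
| 0.3 | 18 / 21 / 28 | 18 | 14 / 18 / 27 | 19 / 22 / 30 |
| 0.5 | 29 / 33 / 41 | 41 | 31 / 41 / 61 | 43 / 51 / 67 |
| 0.6 | 32 / 33 / 38 | 55 | 42 / 55 / 76 | 58 / 66 / 82 |
| 0.8 | 27 / 24 / 21 | 79 | 65 / 79 / 95 | 82 / 88 / 97 |
| 1.0 | 16 / 10 / 7 | 93 | 83 / 93 / 99 | 95 / 98 / >99 |

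**5. Error rate if the better reading is chosen.** P(at least one significant) = (P(final) + P(change) + P(disagree)) / 2. With no effect and ρ = 0.5 this is (5.0 + 5.0 + 8.2) / 2 = 9.1%; it is about 9% across the three correlations.

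**6. Why a baseline covariate settles it.** Write Y = a + τ·arm + β·B + error, with B the baseline score. Subtracting B from both sides gives Y − B = a + τ·arm + (β − 1)·B + error. The treatment coefficient τ, the residuals and the p-value are unchanged, so disagreement is 0%.

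**The case against.** **The plan already adjusts for baseline.** Section 6.2 provides for covariate regression and Section 6.1 allows patients for it. If baseline SF-8 is one of the covariates, the two readings give the same test. This is the strongest reply, and it rules out saying that the plan has no baseline adjustment. But the covariates are not named and the regression is not designated primary over the MANOVA, so the protection is possible rather than specified. The unadjusted t tests above illustrate the two readings; the plan does not name them.

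**The aims never use the word change.** This is correct. The same from-baseline-to-28-days phrase is used for falls in Aim 6a, where it most naturally marks an interval for counting events. A reader might infer two settled and contradictory definitions; the text supports an ambiguity, with change the natural reading for a score measured twice. An unresolved primary outcome still leaves the choice open.

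**Not every outcome is affected.** A reader might extend the split to all outcomes. Falls are most naturally an interval count. For bowel movements, Aim 5a concerns episodes above five a day while Section 1.2 uses the daily average, which is a different discrepancy.

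**Conclusion.** The concern holds as an ambiguity in the primary outcome that the analysis section leaves open, and that also touches ANT, sleep quality and WPAI.

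A reader might conclude that about a third of trials of this size would give conflicting results. The documents do not support that, because size alone does not fix the rate. About a third applies near a true effect of 0.5 to 0.7 SD at a correlation of 0.5. At the roughly 1.0 SD implied by the protocol's own calculation it is 7–16%, and with no effect 8–9%.

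Two results do not depend on picking one effect size. Choosing the favourable reading raises the false-positive rate from 5% to about 9%. And adjustment for baseline had the highest power of the three analyses in every non-null setting tabulated. The gain depends on the correlation: at zero correlation it disappears (54% against 55% for the final value at 0.6 SD), so there is little to lose. All of this assumes normal scores, equal SDs at both times and a baseline measured before randomization.

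That last assumption is not secure in the text. Section 4.2.2 places randomization after baseline procedures, whereas Sections 4.2.1 and 4.2.3 place the baseline assessments after randomization. With no placebo, a self-reported baseline taken after allocation could itself be influenced by the assignment.

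**What to change.** In Sections 1.1, 1.2 and 6.2, state one primary outcome and one primary analysis:

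- **Outcome.** A single named SF-8 score at Day 28. Section 4.1.1 describes physical and mental summary measures and eight domains, so the score must be chosen in advance.
- **Analysis.** Linear regression of that score on arm, with the same score at baseline and the WPAI randomization stratum (≤7 or >7) as covariates. This replaces MANOVA as the primary test.
- **Other outcomes.** The same form for ANT and for the 0–10 WPAI score, with the screening value as baseline. For the four-category sleep item and the fall count, specify a model suited to the type of outcome.
- **Order of procedures.** Reconcile Section 4.2.2 with Sections 4.2.1 and 4.2.3 so that the baseline SF-8 and ANT used as covariates are collected before randomization.

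The cost is protocol and SAP wording. No new data are needed, and Section 6.1 already allows for covariate adjustment. If sites in practice follow the order in Section 4.2.1, the baseline assessments would also have to move ahead of randomization.
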